#### ***9.3.3.2.2. Assessment of causality***

The investigator is obligated to assess the relationship between study vaccine and the occurrence of each AE/SAE using clinical judgement. In case of concomitant administration of multiple vaccines/products, if possible, the investigator should specify if the AE could be causally related to a specific vaccine/product administered (i.e., investigational, control/placebo or co-administered vaccine). When causal relationship to a specific vaccine(s)/product(s) cannot be determined the investigator should indicate the AE to be related to all products.

Alternative plausible causes, such as natural history of the underlying diseases, concomitant therapy, other risk factors, and the temporal relationship of the event to the study vaccine will be considered and investigated. The investigator will also consult the Investigator's Brochure to determine his/her assessment.

There may be situations when a SAE has occurred and the investigator has minimal information to include in the initial report to GSK Biologicals. However, it is very important that the investigator always makes an assessment of causality for every event prior to submission of the Expedited Adverse Events Report to GSK Biologicals. The investigator may change his/her opinion of causality in light of follow-up information and update the SAE information accordingly. The causality assessment is one of the criteria used when determining regulatory reporting requirements.

All solicited local (injection site) reactions will be considered causally related to vaccination. Causality of all other AEs should be assessed by the investigator using the following question: *“Is there a reasonable possibility that the AE may have been caused by the study vaccine?”*

YES: There is a reasonable possibility that the study vaccine contributed to the AE.

NO: There is no reasonable possibility that the AE is causally related to the administration of the study vaccine. There are other, more likely causes and administration of the study vaccine is not suspected to have contributed to the AE.

If an event meets the criteria to be determined as ‘serious’ (see Section 9.1.2), additional examinations/tests will be performed by the investigator in order to determine ALL possible contributing factors for each SAE.

Possible contributing factors include:

- Medical history.
- Other medication.
- Protocol required procedure.
- Other procedure not required by the protocol.
- Lack of efficacy of the vaccine, if applicable.
- Erroneous administration.
- Other cause (specify).

### **9.3.3.3. Assessment of outcomes**

The investigator will assess the outcome of all unsolicited AEs (including SAEs) recorded during the study as:

- Recovered/resolved.
- Recovering/resolving.
- Not recovered/not resolved.
- Recovered with sequelae/resolved with sequelae.
- Fatal (SAEs only).

## 9.4. Reporting of serious adverse events, pregnancies and other events

### 9.4.1. Prompt reporting of serious adverse events, pregnancies and other events to GSK Biologicals

SAEs that occur in the time period defined in Section 9.3 will be reported promptly to GSK within the timeframes described in [Table 23](#), once the investigator determines that the event meets the protocol definition of a SAE.

Pregnancies that occur in the time period defined in Section 9.3 will be reported promptly to GSK within the timeframes described in [Table 23](#), once the investigator becomes aware of the pregnancy.

AEs of specific interest (pIMDs and meningitis) that occur in the time period defined in Section 9.3 will be reported promptly to GSK within the timeframes described in [Table 23](#), once the investigator determines that the event meets the protocol definition of a AEs of specific interest.

**Table 23 Timeframes for submitting serious adverse event, pregnancy and other events reports to GSK Biologicals**

Type of Event	Initial Reports		Follow-up of Relevant Information on a Previous Report	
	Timeframe	Documents	Timeframe	Documents
SAEs	24 hours*#	electronic Expedited Adverse Events Report	24 hours*	electronic Expedited Adverse Events Report
Pregnancies	2 weeks*	electronic pregnancy report	2 weeks*	electronic pregnancy report
AEs of specific interest (pIMDs and meningitis)	24 hours***#	electronic Expedited Adverse Events Report	24 hours*	electronic Expedited Adverse Events Report

\*Timeframe allowed after receipt or awareness of the information.

\*\*Timeframe allowed once the investigator determines that the event meets the protocol definition of a AE of specific interest.

#The investigator will be required to confirm review of the SAE/AE of specific interest causality by ticking the 'reviewed' box in the electronic Expedited Adverse Events Report within 72 hours of submission of the SAE/ AE of specific interest.

### **9.4.3. Completion and transmission of SAE reports to GSK Biologicals**

Once an investigator becomes aware that a SAE has occurred in a study subject, the investigator (or designate) must complete the information in the electronic Expedited Adverse Events Report **WITHIN 24 HOURS**. The report will always be completed as thoroughly as possible with all available details of the event. Even if the investigator does not have all information regarding a SAE, the report should still be completed within 24 hours. Once additional relevant information is received, the report should be updated **WITHIN 24 HOURS**.

The investigator will always provide an assessment of causality at the time of the initial report. The investigator will be required to confirm the review of the SAE causality by ticking the 'reviewed' box in the electronic Expedited Adverse Events Report within 72 hours of submission of the SAE.

#### **9.4.3.1. Back-up system in case the electronic reporting system does not work**

If the electronic reporting system does not work, the investigator (or designate) must complete, then date and sign a paper Expedited Adverse Events Report and fax it to the Study Contact for Reporting SAEs (refer to the [Sponsor Information](#)) or to GSK Biologicals Clinical Safety and Pharmacovigilance department within 24 hours.

This back-up system should only be used if the electronic reporting system is not working and NOT if the system is slow. As soon as the electronic reporting system is working again, the investigator (or designate) must complete the electronic Expedited Adverse Events Report within 24 hours. The final valid information for regulatory reporting will be the information reported through the electronic SAE reporting system.

### **9.4.4. Completion and transmission of pregnancy reports to GSK Biologicals**

Once the investigator becomes aware that a subject is pregnant, the investigator (or designate) must complete the required information onto the electronic pregnancy report **WITHIN 2 WEEKS**.

Note: Conventionally, the estimated gestational age (EGA) of a pregnancy is dated from the first day of the last menstrual period (LMP) of the cycle in which a woman conceives. If the LMP is uncertain or unknown, dating of EGA and the estimated date of delivery should be estimated by ultrasound examination and recorded in the pregnancy report.

### **9.4.5. Reporting of AEs of specific interest to GSK Biologicals**

Once a AE of specific interest (pIMD and meningitis) is diagnosed (serious or non-serious) in a study subject, the investigator (or designate) must complete the information in the electronic Expedited Adverse Events Report **WITHIN 24 HOURS** after he/she becomes aware of the diagnosis. The report allows to specify that the event is a pIMD and whether it is serious or non-serious. The report will always be completed as thoroughly as possible with all available details of the event, in accordance with the pIMD standard questionnaire provided. Even if the investigator does not have all

information regarding a AE of specific interest, the report should still be completed within 24 hours. Once additional relevant information is received, the report should be updated **WITHIN 24 HOURS**.

The investigator will always provide an assessment of causality at the time of the initial report. The investigator will be required to confirm the review of the AE of specific interest causality by ticking the 'reviewed' box in the electronic Expedited Adverse Events Report within 72 hours of submission of the AE of specific interest.

Refer to Section 9.4.3.1 for back-up system in case the electronic reporting system does not work.

#### **9.4.6. Updating of SAE, pregnancy and AE of specific interest information after removal of write access to the subject's eCRF**

When additional SAE, pregnancy or AE of specific interest information is received after removal of the write access to the subject's eCRF, new or updated information should be recorded on the appropriate paper report, with all changes signed and dated by the investigator. The updated report should be faxed to the Study Contact for Reporting SAEs (refer to the [Sponsor Information](#)) or to GSK Biologicals Clinical Safety and Pharmacovigilance department within the designated reporting timeframes specified in [Table 23](#).

#### **9.4.7. Regulatory reporting requirements for serious adverse events**

The investigator will promptly report all SAEs to GSK in accordance with the procedures detailed in Section 9.4.1. GSK Biologicals has a legal responsibility to promptly notify, as appropriate, both the local regulatory authority and other regulatory agencies about the safety of a product under clinical investigation. Prompt notification of SAEs by the investigator to the Study Contact for Reporting SAEs is essential so that legal obligations and ethical responsibilities towards the safety of other subjects are met.

Investigator safety reports are prepared according to the current GSK policy and are forwarded to investigators as necessary. An investigator safety report is prepared for a SAE(s) that is both attributable to the study vaccine and unexpected. The purpose of the report is to fulfil specific regulatory and GCP requirements, regarding the product under investigation.

### **9.5. Follow-up of adverse events, serious adverse events and pregnancies**

#### **9.5.1. Follow-up of adverse events and serious adverse events**

##### **9.5.1.1. Follow-up during the study**

After the initial AE/SAE report, the investigator is required to proactively follow each subject and provide additional relevant information on the subject's condition to GSK Biologicals (within 24 hours for SAEs; refer to [Table 23](#)).

All SAEs and AE of specific interest (pIMDs and meningitis) (serious or non-serious) documented at a previous visit/contact and designated as not recovered/not resolved or recovering/resolving will be reviewed at subsequent visits/contacts until the last visit of the subject.

All AEs documented at a previous visit/contact and designated as not recovered/not resolved or recovering/resolving will be reviewed at subsequent visits/contacts until 30 days after vaccination/challenge, as applicable.

#### **9.5.1.2. Follow-up after the subject is discharged from the study**

The investigator will follow subjects:

- With SAEs, AE of specific interest (pIMDs or meningitis) (serious or non-serious), or subjects withdrawn from the study as a result of an AE, until the event has resolved, subsided, stabilized, disappeared, or until the event is otherwise explained, or the subject is lost to follow-up.

If the investigator receives additional relevant information on a previously reported SAE, he/she will provide this information to GSK Biologicals using a paper/electronic Expedited Adverse Events Report and/or pregnancy report as applicable.

GSK Biologicals may request that the investigator performs or arranges the conduct of additional clinical examinations/tests and/or evaluations to elucidate as fully as possible the nature and/or causality of the AE or SAE. The investigator is obliged to assist. If a subject dies during participation in the study or during a recognized follow-up period, GSK Biologicals will be provided with any available post-mortem findings, including histopathology.

#### **9.5.2. Follow-up of pregnancies**

Pregnant subjects will be followed to determine the outcome of the pregnancy. At the end of the pregnancy, whether full-term or premature, information on the status of the mother and child will be forwarded to GSK Biologicals using the electronic pregnancy report and the Expedited Adverse Events Report if applicable. Generally, the follow-up period does not need to be longer than six to eight weeks after the estimated date of delivery.

Regardless of the reporting period for SAEs for this study, if the pregnancy outcome is a SAE, it should always be reported as SAE.

### **9.6. Treatment of adverse events**

Treatment of any AE is at the sole discretion of the investigator and according to current good medical practice. Any medication administered for the treatment of a SAE/AE of specific interest (pIMDs and meningitis) should be recorded in Expedited Adverse Event Report of the subject's eCRF (refer to Section 7.6).

## **9.7. Subject card**

Study subjects must be provided with the address and telephone number of the main contact for information about the clinical study.

The investigator (or designate) must therefore provide a “subject card” to each subject. In an emergency situation this card serves to inform the responsible attending physician that the subject is in a clinical study and that relevant information may be obtained by contacting the investigator.

Subjects must be instructed to keep subject cards in their possession at all times during the study duration.

## 10. SUBJECT COMPLETION AND WITHDRAWAL

### 10.1. Subject completion

A subject who returns for the concluding visit foreseen in the protocol is considered to have completed the study.

### 10.2. Subject withdrawal

Withdrawals will not be replaced.

#### 10.2.1. Subject withdrawal from the study

From an analysis perspective, a 'withdrawal' from the study refers to any subject who did not come back for the concluding visit foreseen in the protocol.

All data collected until the date of withdrawal/last contact of the subject will be used for the analysis.

A subject is considered a 'withdrawal' from the study when no study procedure has occurred, no follow-up has been performed and no further information has been collected for this subject from the date of withdrawal/last contact.

Investigators will make an attempt to contact those subjects who do not return for scheduled visits or follow-up.

Information relative to the withdrawal will be documented in the eCRF. The investigator will document whether the decision to withdraw a subject from the study was made by the subject himself/herself, or by the investigator, as well as which of the following possible reasons was responsible for withdrawal:

- SAE.
- Unsolicited non-serious AE.
- Solicited AE.
- Protocol violation (specify).
- Consent withdrawal, not due to an AE\*.
- Moved from the study area.
- Lost to follow-up.
- Other (specify).

\*In case a subject is withdrawn from the study because he/she has withdrawn consent, the investigator will document the reason for withdrawal of consent, if specified by the subject, in the eCRF.

Subjects who are withdrawn from the study because of SAEs/AEs must be clearly distinguished from subjects who are withdrawn for other reasons. Investigators will

follow subjects who are withdrawn from the study as result of a SAE/AE until resolution of the event (see Section 9.5.1.2).

### 10.3. Screen and baseline failures

Screening failures are defined as subjects who are withdrawn from the study after giving informed consent, but who do not meet the inclusion criteria. Reason for screening failure will be collected.

## 11. STATISTICAL METHODS

### 11.1. Primary endpoint

- Occurrence of *P. falciparum* parasitemia (defined by a positive blood slide) following sporozoite challenge (in all study groups versus infectivity controls).

### 11.2. Secondary endpoints

#### *Efficacy*

- Time-to-onset of *P. falciparum* parasitemia (defined by a positive blood slide) following sporozoite challenge.

#### *Immunogenicity*

- Anti-CS repeat region antibody concentrations at screening, Day 1, prior to challenge (Day 22), 28 days post-challenge (Day 50) and at study end (Day 190).
- Anti-HBs IgG antibody concentrations at screening, Day 1, prior to challenge (Day 22), 28 days post-challenge (Day 50) and at study end (Day 190).

#### *Safety*

- Occurrence of solicited local and general AEs within 7 days after vaccination (day of vaccination and 6 subsequent days) in the booster vaccination groups.
- Occurrence of unsolicited AEs up to 21 days after vaccination (day of vaccination and 20 subsequent days), according to the Medical Dictionary for Regulatory Activities (MedDRA) classification, in the booster vaccination groups.
- Occurrence of AEs up to 29 days after challenge (day of challenge and 28 subsequent days), according to the MedDRA classification, in all study groups.
- Occurrence of AEs of specific interest (potential immune-mediated diseases [pIMDs] and meningitis) from Day 1 up to study conclusion (Day 190), according to the MedDRA classification, in all study groups.
- Occurrence of SAEs (all, fatal, related to investigational vaccine) during the whole study period (from screening up to study conclusion [Day 190]), according to the MedDRA classification, in all study groups.

- Occurrence of abnormal laboratory values at screening, Day 1, Day 8, Day 22, the day of first parasitemia and 28 days post-challenge (Day 50) for the booster vaccination groups; and at screening, Day 22, the day of first parasitemia and 28 days post-challenge (Day 50) for the infectivity control subjects.

### 11.3. Tertiary endpoints

#### *Efficacy*

- Occurrence of *P. falciparum* parasitemia (defined by a positive blood slide) following sporozoite challenge (between study groups).
- Time-to-onset of *P. falciparum* parasitemia (defined by a positive blood slide) following sporozoite challenge (between study groups).
- Occurrence of *P. falciparum* parasitemia (defined by a positive PCR) following sporozoite challenge (between study groups).
- Time-to-onset of *P. falciparum* parasitemia (defined by a positive PCR) following sporozoite challenge (between study groups).

#### *Immunogenicity*

- Anti-CS repeat region IgG avidity index at Day 1, prior to challenge (Day 22), 28 days post-challenge (Day 50) and at study end (Day 190).
- Anti-full length CS protein IgG concentrations and anti-C-term IgG concentrations at Day 1, prior to challenge (Day 22), 28 days post-challenge (Day 50) and at study end (Day 190).
- Anti-full length CS protein and anti-C-term IgG avidity at Day 1, prior to challenge (Day 22), 28 days post-challenge (Day 50) and at study end (Day 190).

### 11.4. Determination of sample size

The target enrollment for the MALARIA-092 study was ~130 vaccinated subjects (~26/vaccine group) and up to 30 subjects (or 4-6 per day, depending on the expected number of days of challenge) in the infectivity control group. Approximately 20 subjects in each group were expected to undergo sporozoite challenge (~100 vaccinated subjects overall). Based on past experience, an approximate 20% will refuse to participate in the booster study and there will be an approximate 20% drop-out rate in vaccinees for the booster study. With an assumed vaccine efficacy (VE) of ~68% in the primary study, there will be a minimum of ~20 subjects per group in this MALARIA-102 study. In addition, up to 24 infectivity control subjects will be newly enrolled for this study.

Assuming at least 19/20 controls and 6/20 vaccinees become positive (VE of ~68%), the trial has 99% power to detect statistically significant vaccine efficacy of each of the vaccination groups over the infectivity controls (p-value < 0.05).

The power to detect a statistically significant VE of each of the vaccination groups over the infectivity controls (p-value < 0.05) is presented in the table below:

Controls (N)	Vaccines (N)	Vaccine efficacy (%)	Protected controls (N)	Protected vaccinees (N)	Power* (%)
20	20	89	1	18	100
20	20	78	1	16	100
20	20	68	1	14	99.1
20	20	58	1	12	94.6
20	20	47	1	10	81.8

\*Two independent proportions power analysis - Test statistic: Fisher exact test

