## 11.9. Analysis of efficacy

The analysis of efficacy will be performed on the PPS for analysis of immunogenicity and efficacy.

Efficacy will be assessed by comparison of *P. falciparum* parasitemia incidence and time-to-onset of *P. falciparum* parasitemia after sporozoite challenge. The analysis of the primary objective will be based on blood smears results; additional exploratory analyses will be performed based PCR results (tertiary objectives).

Vaccine efficacy (VE) is defined as  $100 * (1 - \text{Relative Risk})$ . Relative risk of infection and 95% CI will be calculated.

Fisher's Exact test will be used for the comparison of *P. falciparum* parasitemia incidence after challenge between each one of the study groups (P-Fx and NP-Fx) and the infectivity control group.

Kaplan-Meier analysis will be performed on time-to-onset of *P. falciparum* parasitemia, for comparisons between each one of the study groups (P-Fx and NP-Fx) and the infectivity control group, using the log-rank statistic.

The same methodology will be applied for the evaluation of the study groups (P-Fx vs. NP-Fx) versus each other. If there are sufficient evaluable subjects to draw some conclusions, descriptive analyses based on initial group assignment versus control will be performed.

All statistical tests will be two-tailed at 5% significance level.

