## 11.12. Interpretation of analyses

All analyses performed during this study will be descriptive. The inferential analyses will not be considered confirmatory but rather used as an estimation of the probability that an effect is true.

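### The power table in Protocol 11.4 is labelled p < 0.05, but its figures belong to a two-sided 0.025 test and so understate power at the planned 5% level

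*Protocol*

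**What the plan says.** Protocol 11.4 gives a headline and a five-row table. The headline reads: "Assuming at least 19/20 controls and 6/20 vaccinees become positive (VE of ~68%), the trial has 99% power", followed by the condition that p is below 0.05. The table is introduced as "The power to detect a statistically significant VE of each of the vaccination groups over the infectivity controls (p-value < 0.05"), and its footnote names the method: "Two independent proportions power analysis - Test statistic: Fisher exact test". Every row has 20 controls, 20 vaccinees and 1 protected control. Protected vaccinees number 18, 16, 14, 12 and 10, and the printed power is 100, 100, 99.1, 94.6 and 81.8%.

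The analysis sections match the label. Protocol 11.9 plans the same test ("Fisher's Exact test will be used for the comparison of *P. falciparum* parasitemia incidence after challenge between each one of the study groups") and fixes the level: "All statistical tests will be two-tailed at 5% significance level". SAP 5.3.1 repeats both. Neither section splits the level across the comparisons of P-Fx and NP-Fx with controls. On interpretation, Protocol 11.12 says "All analyses performed during this study will be descriptive", and SAP section 6 says the same.

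**The concern.** All the inputs to the table are printed, so it can be checked exactly, and at the level on its label it does not check. The last row is 7.6 points away from the value for the stated test, which is too far to be rounding.

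What is at stake is that the printed power should describe the test the trial will run. The lower rows matter most to a reader judging what the study could detect if efficacy is modest, which is plausible in NP-Fx, whose members were not protected at their first challenge. At a vaccine efficacy of 47%, that reader is told the risk of missing the effect is 18.2% (100 − 81.8). Under the planned test it is 10.6% (100 − 89.4).

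**Working it through.** **Inputs, all from Protocol 11.4.** n = 20 controls and 20 vaccinees. Control infection rate 19/20 = 0.95. Vaccinee infection rate q = (20 − protected)/20 = 0.10, 0.20, 0.30, 0.40, 0.50.

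**Formula.** Let X be infected controls and Y infected vaccinees, independent binomials. Then

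power(α) = Σₓ Σᵧ P(X = x) · P(Y = y) · 1[two-sided Fisher p(x, y) < α],

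summed over all 21 × 21 outcomes.

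**Results (%).**

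| Protected vaccinees | q | Printed | Two-sided 0.05 | Two-sided 0.025 | Understatement at 0.05 (points) |
|---|---|---|---|---|---|
| 18 | 0.10 | 100 | 100.0 | 100.0 | 0 |
| 16 | 0.20 | 100 | 99.98 | 99.95 | 0 |
| 14 | 0.30 | 99.1 | 99.66 | 99.12 | 99.7 − 99.1 ≈ 0.5 (unrounded 99.66 − 99.12) |
| 12 | 0.40 | 94.6 | 97.44 | 94.59 | 97.4 − 94.6 = 2.8 |
| 10 | 0.50 | 81.8 | 89.40 | 81.79 | 89.4 − 81.8 = 7.6 |

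The 0.025 column reproduces every printed value to its printed precision. The 0.05 column does not reproduce the last three.

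**Last row by hand (q = 0.50).** For each number of infected controls x, the table gives the largest y that is still significant in favour of the vaccine.

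| x | P(X = x) | Largest y, p < 0.05 (its p) | P(Y ≤ y) | Product | Largest y, p < 0.025 (its p) | P(Y ≤ y) | Product |
|---|---|---|---|---|---|---|---|
| 20 | 0.3585 | 15 (0.047) | 0.9941 | 0.3564 | 14 (0.020) | 0.9793 | 0.3511 |
| 19 | 0.3774 | 13 (0.044) | 0.9423 | 0.3556 | 12 (0.020) | 0.8684 | 0.3277 |
| 18 | 0.1887 | 11 (0.031) | 0.7483 | 0.1412 | 10 (0.014) | 0.5881 | 0.1110 |
| 17 | 0.0596 | 10 (0.041) | 0.5881 | 0.0350 | 9 (0.019) | 0.4119 | 0.0245 |
| 16 | 0.0133 | 9 (0.048) | 0.4119 | 0.0055 | 8 (0.023) | 0.2517 | 0.0034 |
| ≤ 15 | 0.0026 | | | 0.0003 | | | 0.0003 |
| Sum | | | | **0.894** | | | **0.818** |

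In each of the five main lines, the stricter level moves the cut-off by one infected vaccinee. That is the whole difference between 89.4 and 81.8.

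**Other explanations tried, last row (printed 81.8).**

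- Fisher one-sided 0.05: 94.3.
- Fisher one-sided 0.025: 89.4, the same as two-sided 0.05, so confusing one-sided with two-sided does not explain the table.
- Fisher one-sided 0.0125: 81.8, numerically the same test as two-sided 0.025.
- Fisher two-sided 0.01: 71.5.
- Pooled z: 92.2 at two-sided 0.05, 86.3 at 0.025.
- Unpooled z: 95.8 at two-sided 0.05.
- Continuity-corrected z: 84.4 at 0.05, 75.3 at 0.025.
- Arcsine with correction: 86.3 at 0.05, 79.2 at 0.025.
- Fisher two-sided 0.05 with 18, 19 or 24 controls: 90.6, 90.1, 92.7.

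Only a Fisher test at two-sided 0.025, or its one-sided equivalent, fits the whole table.

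**The case against.** The strongest reply is that nothing the trial depends on is affected. This largely stands. The true power is higher than printed in every row that differs. The one scenario the text relies on, efficacy of about 68%, has 99.7% power at 5%, so the headline of 99% remains true as a floor. The 7.6-point gap is in the most pessimistic row, where power exceeds 80% at either level. Nor does the table fix enrolment: Protocol 5.1 takes all willing MALARIA-092 subjects, possibly more or fewer than 40, and the controls may number 6 to 24. At 5% and 47% efficacy, power with 20 vaccinees is 79.1% with 12 controls and 92.7% with 24. Realised numbers can therefore move power by more than the mislabelling does. None of this makes the printed figures right for the stated test.

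A reader might also infer two stronger things, and the documents support neither.

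- **That the trial was sized for a 2.5% split over the two primary comparisons and the analysis section then lost it.** Half of 0.05 is what such a split would give. But no section mentions 2.5% or a multiplicity adjustment, and halving the level by mistake in software that is already two-sided would leave the same figures. The match shows which level was used, not why.
- **That the significance threshold for P-Fx and NP-Fx is now ambiguous.** It is not. Protocol 11.4, Protocol 11.9 and SAP 5.3.1 all say 5%, and an analyst following them would test each group at 5%. Only the power figures are out of step.

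**Conclusion.** The mismatch is certain: the table's label and its figures belong to different significance levels. At the two-tailed 5% level the plan fixes, power is 100, 100, 99.7, 97.4 and 89.4%, and the table understates it by 0.5, 2.8 and 7.6 points in the last three rows. This rests only on the protocol's own inputs (20 per group, 95% control infection, independent binomial outcomes) and on its named test.

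The importance is minor. The error is conservative, the sample size and the headline stand, and the tests are declared non-confirmatory. The documents give no reason for 0.025, and no change to the analysis level follows from this finding.

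**What to change.** In Protocol 11.4, do one of the following:

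1. Reprint the power column for the two-sided 5% Fisher test (100, 100, 99.7, 97.4, 89.4) and give the headline as 99.7%. This is preferable, because the table then describes the planned test.
2. Keep the figures, label the table and the headline as two-sided 0.025, and say why that level was used.

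Leave Protocol 11.9 and SAP 5.3.1 at 5% unless the sponsor confirms that a split across the two comparisons with controls was intended.

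The cost is one table column and one sentence. Subjects, procedures and analyses do not change.
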